### **5.4 Follow-up Procedures**

Patients will be followed for at least 30 days after surgery. Follow-up will consist of postoperative visit or telephone call (in situations where there is no postoperative visit  $\geq$  30 days from surgery).

### **5.5 Removal of Subjects from Study Treatment and Study**

Patients can be taken off the study treatment and/or study at any time at their own request, or they may be withdrawn at the discretion of the investigator for safety, behavioral or administrative reasons. The reason(s) for discontinuation will be documented and may include:

**5.5.1** Patient completed study treatment;

**5.5.2** Patient voluntarily withdraws from treatment (follow-up permitted);

**5.5.3** Patient withdraws consent (termination of treatment and follow-up);

**5.5.4** Patient is unable to comply with protocol requirements (i.e. the patient is unable to tolerate or misses more than 50% of the study drug doses);

**5.5.5** Patient experiences toxicity that makes continuation in the protocol unsafe;

**5.5.6** Treating physician judges continuation on the study would not be in the patient's best interest;

**5.5.7** Patient becomes pregnant (pregnancy to be reported along same timelines as a

serious adverse event);

#### **5.5.8 Lost to follow-up.**

If a research subject cannot be located to document adverse events after a period of at 60 days after surgery, the subject may be considered “lost to follow-up.” All attempts to contact the subject during this period will be documented.

## **6.0 Measurement of Effect**

---

### **6.1 Effect on Return of Bowel Function**

Time to first flatus, time to first BM, time to tolerance of solid diet will all be measured as endpoints for return of bowel function.

Time to flatus is a more subjective and unreliable endpoint for return of lower bowel function versus time to first BM. More recent alvimopan studies have used GI-2 rather than GI-3 endpoints, which consider BM rather than flatus as evidence of lower bowel function. Thus, the current study will use the GI-2 definition, which is the time, in hours, from leaving the operating room to the later of the time of tolerating solid food and having a BM. Tolerance of solid food is defined as the time of solid food ingestion without significant nausea or vomiting for 4 hours. The precise date and hour of first flatus, first BM, and first tolerance of solid diet will be recorded in a participant diary (Appendix B). These dates and times will be corroborated and audited by reviewing the inpatient medical record (in  $\geq 10\%$  of participants).

#### **6.1.1 Prolonged Ileus**

Participants without flatus or BM for more than seven days after surgery, are considered to have a prolonged ileus.

#### **6.1.2 Time to Hospital Discharge**

The time, in hours, from leaving the operating room to when the discharge order is signed.

### **6.2 Safety/tolerability**

Analyses will be performed for all patients having received at least one dose of study drug. The study will use the CTCAE version 4.03 (<http://ctep.cancer.gov/reporting/ctc.html>) for reporting of adverse events.

## **7.0 ADVERSE EVENTS**

---

An adverse event (AE) is any untoward medical occurrence in a patient receiving study treatment and which does not necessarily have a causal relationship with this treatment. An AE can therefore be any unfavorable and unintended sign (including an abnormal laboratory finding), symptom, or disease temporally associated with the use of an experimental intervention, whether or not related to the intervention.

### **7.1 Adverse Event Monitoring**

Adverse event data collection and reporting, which are required as part of every clinical

trial, are done to ensure the safety of subjects enrolled in the studies as well as those who will enroll in future studies using similar agents. Adverse events are reported in a routine manner at scheduled times during a trial. Additionally, certain adverse events must be reported in an expedited manner to allow for optimal monitoring of patient safety and care.

As far as possible, each adverse event should be evaluated to determine:

- duration (start and end dates)
- severity (grade)
- seriousness
- relationship to study agent
- action taken (i.e., none, study agent modification, medical intervention)
- outcome (i.e., resolved without sequelae, resolved with sequelae, ongoing)

All patients experiencing an adverse event, regardless of its relationship to study drug, will be monitored until:

- the adverse event resolves or the symptoms or signs that constitute the adverse event return to baseline;
- any abnormal laboratory values have returned to baseline;
- there is a satisfactory explanation other than the study drug for the changes observed; or
- death.

## 7.2 Severity

All adverse events will be graded according to the NCI Common Terminology Criteria for Adverse Events (CTCAE) version 4.03. The CTCAE v4.03 is available at <http://ctep.cancer.gov/reporting/ctc.html>

If no CTCAE grading is available, the severity of an AE is graded as follows:

Mild (grade 1): the event causes discomfort without disruption of normal daily activities.

Moderate (grade 2): the event causes discomfort that affects normal daily activities.

Severe (grade 3): the event makes the patient unable to perform normal daily activities or significantly affects his/her clinical status.

Life-threatening (grade 4): the patient was at risk of death at the time of the event.

Fatal (grade 5): the event caused death.

## 7.3 Seriousness

A “serious” adverse event is defined in regulatory terminology as any untoward medical occurrence that:

1. Results in death.  
If death results from (progression of) the disease, the disease should be reported as event (SAE) itself.
2. Is life-threatening.  
(the patient was at risk of death at the time of the event; it does not refer to an event that hypothetically might have caused death if it were more severe).

3. Requires in-patient hospitalization or prolongation of existing hospitalization for  $\geq$  24 hours.
4. Results in persistent or significant disability or incapacity.
5. Is a congenital anomaly/birth defect
6. Is an important medical event

Any event that does not meet the above criteria, but that in the judgment of the investigator jeopardizes the patient, may be considered for reporting as a serious adverse event. The event may require medical or surgical intervention to prevent one of the outcomes listed in the definition of "Serious Adverse Event".

For example: allergic bronchospasm requiring intensive treatment in an emergency room or at home; convulsions that may not result in hospitalization; development of drug abuse or drug dependency.

#### 7.4 Relationship

Attribution categories for adverse events in relationship to protocol therapy are as follows:

Definite – The AE *is clearly related* to the study treatment.

Probable – The AE *is likely related* to the study treatment.

Possible – The AE *may be related* to the study treatment.

Unlikely – The AE *is doubtfully related* to the study treatment.

Unrelated – The AE *is clearly NOT related* to the study treatment.

#### 7.5 Prior experience

Expected events are those that have been previously identified as resulting from administration of the agent. An adverse event is considered unexpected, for expedited reporting purposes only, when either the type of event or the severity of the event is not listed in the current known adverse events listed in the agent clinical experience section of this protocol or the current Product Label.

#### 7.6 Reporting Requirements for Adverse Events

##### 7.6.1 Expedited Reporting

- The **Principal Investigator** must be notified within 24 hours of learning of any serious adverse events, regardless of attribution, occurring during the study or within 30 days of the last administration of the study drug.
- The **UCSD Human Research Protections Program (HRPP)** must be notified within 10 business days of "any unanticipated problems involving risk to subjects or others" (UPR).

The following events meet the definition of UPR:

1. Any serious event (injuries, side effects, deaths or other problems), which in the opinion of the Principal Investigator was unanticipated, involved risk to subjects or others, and was possibly related to the research procedures.
2. Any serious accidental or unintentional change to the IRB-approved protocol that alters the level of risk.
3. Any deviation from the protocol taken without prior IRB review to eliminate apparent immediate hazard to a research subject.
4. Any new information (e.g., publication, safety monitoring report,

updated sponsor safety report), interim result or other finding that indicates an unexpected change to the risk/benefit ratio for the research.

5. Any breach in confidentiality that may involve risk to the subject or others.
6. Any complaint of a subject that indicates an unanticipated risk or that cannot be resolved by the Principal Investigator.

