##### **4.1 Treatment Dosage and Administration**

Participants will receive alvimopan (or placebo) preoperatively, then every day after surgery until hospital discharge or for a maximum of 7 days.

Twelve (12) mg of alvimopan (or placebo) will be given by mouth in the preoperative holding area 30 minutes to 5 hours prior to surgery. The treatment will continue at a dose of 12 mg BID by mouth starting on postoperative day (POD) 1 for the earlier of seven days or hospital discharge, as defined by GI-2 (later of time of tolerance of solid diet or bowel movement), for a maximum of 15 total doses. In patients with a gastrostomy tube in place, this will be clamped for 1 hour after administration of the study drug per standard of care for oral medication administration in a patient with a gastrostomy tube. Documentation of gastrostomy tube clamping after study drug administration will be made in the medical record by nurses according to the standard of care nursing policies and usual practices of each nursing unit. The study drug (alvimopan or placebo) will be administered in the hospital by the patient's nurse.

Agent	Dose	Route	Schedule
Alvimopan	12 mg	PO	30 minutes – 5 hours prior to surgery, then twice daily (BID) starting POD 1 for a maximum of 7 days or until hospital discharge
Placebo	NA	PO	30 minutes – 5 hours prior to surgery, then twice daily (BID) starting POD 1 for a maximum of 7 days or until hospital discharge

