#### **4.6 Duration of Therapy**

In the absence of treatment delays due to adverse events, treatment may continue for a maximum of **seven days** or less if one of the following occurs:

- Participant is discharged home prior to seven days after surgery

- Inter-current illness that prevents further administration of treatment (i.e. participant is unable to tolerate oral medication with gastric tube clamped or the participant is intubated and cannot take oral medication). Participants may resume study drug administration once it can be tolerated without “make-up” doses given (i.e. no study drug will be given beyond postoperative day seven). If more than 50% of the doses are missed, then the participant will be withdrawn from the study (see Section 5.5).
- Unacceptable adverse event(s)
- Participant decides to withdraw from the study, **OR**
- General or specific changes in the patient’s condition render the patient unacceptable for further treatment in the judgment of the investigator.

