#### 4.7 Duration of Follow Up

Participants will be monitored daily during their postoperative stay by nurses and physicians, per standard of care after CRS/HIPEC. Typical length of stay after this procedure is 10 days. After discharge, participants will be followed (by postoperative visit or telephone call) for 30 days from the date of surgery for adverse events.

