#### 5.1 Schedule of Events

	Screening (POD -30 to -1)	Preoperative Day (POD -3 to -1)	Postoperative Admission (POD 1 – Date of Discharge)	Postoperative Clinic Visit ± 5 days	Follow-up visit (POD ≥ 30) 
Assessment					
Informed consent	X				
Medical history	X				
Physical exam, including vitals 	X				
Demographic	X				
Eligibility Criteria	X				
ECOG	X				
Adverse events 			X	X	X
Concomitant medications 	X	X			
Confirmation that CRS/HIPEC performed and eligibility criteria still met 			X		
Assessment of return of bowel function 			X		
Alvimopan administration 		X	X		
Urine Pregnancy Test 	X				

By standard of care clinic visit, or telephone call if no clinic visit at this time (≥ 30 days)

after surgery)

Physical exam and vital signs: consist of temperature, heart rate, respiration and blood pressure.

Adverse events: to be collected once patient signs consent form. See Section 7 for more information.

Concomitant medications: to be collected for any subject being followed for a Serious Adverse Event (SAE) occurring up to 30 days after last dose of study drug until resolution of the SAE. (see Section 7).

Confirmed on POD 1, prior to administration of first postoperative dose of study medication.

Includes recording the date and hour of the time of first flatus, bowel movement, and tolerance of solid food (per participant diary); as well as the date/hour of leaving the operating room

Alvimopan administration: see section 8.1 for instructions on administration.

Pregnancy test: A serum or urine pregnancy test is required for all females of childbearing potential.

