### **5.2.5 Review previous and concomitant medications**

All prior medication taken by the subject within 4 weeks before starting the study is to be recorded. Concomitant medications taken by the subject during the study are to be recorded up until 30-days after last study dose. If a reportable adverse event (see Section 7) occurs within 30-days after last study dose, recording of concomitant medications should continue until resolution of the adverse event.

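### SAE and concomitant-medication windows run to 30 days after the last dose (up to POD 37), but the last required contact may fall on POD 30, so up to 7 days have no guaranteed contact

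*Combined protocol and SAP*

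**What the plan says.** The protocol runs two clocks.

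**Counted from the last dose**
- Section 7.6.1: the principal investigator "must be notified within 24 hours of learning of any serious adverse events", whatever the attribution, if they occur during the study or "within 30 days of the last administration of the study drug".
- Section 5.2.5: "Concomitant medications taken by the subject during the study are to be recorded up until 30-days after last study dose". Footnote 4 of the schedule in Section 5.1 uses the same anchor, but only for patients being followed for an SAE.

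**Counted from surgery**
- Section 4.7: after discharge, participants are followed by visit or call "for 30 days from the date of surgery for adverse events".
- Section 5.4: "Patients will be followed for at least 30 days after surgery".
- Section 5.1: the last column with an adverse-event assessment is headed "Follow-up visit (POD ≥ 30" (closing bracket omitted here). It has no upper limit. Footnote 1 lets a routine clinic visit serve, with a telephone call if there is none.

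**How long dosing can last**
- Section 4.1: one preoperative dose, then twice daily from POD 1, "for a maximum of 15 total doses".
- Section 4.6: "no study drug will be given beyond postoperative day seven".

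Section 5.5.8 adds that a patient who cannot be located to document adverse events may be called lost to follow-up after 60 days from surgery.

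**The concern.** The reporting duty and the means of meeting it end on different days. A patient who takes any dose after surgery has an SAE window that closes after POD 30. Staff who make the final call on POD 30 have done all that Sections 4.7, 5.1 and 5.4 require. After that call nothing scheduled would bring a new event to light, and Section 7.6.1 takes effect only once someone learns of one. Late SAEs would then be recorded only if they happened to become known, for example through a readmission to the same hospital.

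The same gap touches concomitant medications. Section 5.2.5 asks for a record to 30 days after the last dose, and a final contact on POD 30 cannot supply that for anyone dosed after surgery.

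What is at stake is the completeness of the safety record in the days just after POD 30. The efficacy comparison is not involved.

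**Working it through.** **Inputs**
- Preoperative doses: 1, on the day of surgery (Section 4.1).
- Postoperative doses: 2 per day from POD 1 (Section 4.1), none after POD 7 (Section 4.6).
- Length of the SAE and concomitant-medication windows: 30 days after the last dose (Sections 7.6.1 and 5.2.5).
- Earliest final contact that complies: POD 30 (Sections 5.1 and 5.4; Section 4.7 also counts 30 days from surgery).

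**Step 1. Reproduce the plan's own figure.** 1 + 2 × 7 = 15 doses. This matches the stated maximum and confirms POD 7 as the latest dosing day.

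**Step 2. End of the window.** With the last dose on POD L, the window closes on POD L + 30. For L = 7 this is POD 37.

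**Step 3. Days without a required contact.** With the final contact on POD C, the gap is max(0, L + 30 − C).

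Contact on POD 30, varying the last dose:

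| Last dose (POD) | Window closes (POD) | Gap (days) |
|---|---|---|
| 0 (preoperative dose only) | 30 | 0 |
| 1 | 31 | 1 |
| 3 | 33 | 3 |
| 5 | 35 | 5 |
| 7 | 37 | 7 |

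Last dose on POD 7, varying the contact:

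| Final contact (POD) | Gap (days) |
|---|---|
| 30 | 7 |
| 33 | 4 |
| 35 | 2 |
| 37 or later | 0 |

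The maximum is 7 of the 37 days after surgery, or 7/37 = 19%.

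**Step 4. How many patients might be dosed to POD 7.** The documents do not fix this, so the answer is a range resting on assumptions.
- If dosing runs to the earlier of seven days or actual discharge, the 10-day median stay in Section 1.1 means at least half of patients would still be in hospital on POD 7, if stays resemble past practice and dosing is not stopped for other reasons.
- Section 4.1 also links the discharge endpoint of dosing to GI-2 recovery. If dosing stops at GI-2, take the planning medians of 5.7 and 9 days (Section 9.2) and assume exponential times. The share still being dosed at day 7 is then 2^(−7/5.7) ≈ 43% on alvimopan and 2^(−7/9) ≈ 58% on placebo, about half overall.

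On either reading a last dose on POD 7 would be common. How often the final contact would fall close to POD 30 cannot be told from the documents.

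**The case against.** The strongest reply is that POD 30 is a minimum. Section 5.4 and the schedule set no upper limit, and Section 5.5.8 contemplates attempts to reach a patient up to 60 days after surgery. A contact on POD 37 or later already complies and would cover the whole window. This stands, and it rules out the stronger reading that a reader might take from Section 4.7 alone, namely that follow-up stops on POD 30 and the last week has no contact at all. It does not remove the gap: a later contact is permitted but not required, and Section 5.5.8 only says when an unlocatable patient may be declared lost.

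Second, Section 7.6.1 is a duty to notify, not a surveillance schedule, and a passive reporting window may outlast active follow-up. That is fair for SAEs: a late event that becomes known is still reportable. It does not answer Section 5.2.5, which asks for data that a POD 30 contact cannot provide.

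Third, a reader might infer that ascertainment differs between arms because the gap grows with treatment duration, which is related to recovery. The documents do not support this. The surgery anchor gives every patient in both arms the same minimum follow-up, and what varies is only the share of a reporting window that is covered. Section 9.9 also frames the safety analysis around the intervention period, and nothing shows that events on POD 31–37 would enter a comparison of arms.

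Finally, it would be wrong to suppose that everyone who stops dosing early is fully covered by a POD 30 contact. That holds only for patients who took just the preoperative dose.

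**Conclusion.** The inconsistency is real and minor. The windows in Sections 7.6.1 and 5.2.5 can extend beyond the earliest compliant final contact by 0 to 7 days. Seven days is a ceiling that needs both a last dose on POD 7 and a contact on POD 30. The weakness lies in active ascertainment: the plan guarantees no contact in that interval, though it does not forbid one.

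The primary endpoint, alpha and power are unaffected, and no between-arm bias is shown. The gap itself rests only on day counts from the protocol. Its frequency rests on the assumptions in Step 4 and on when contacts are actually made, which the documents do not state. It merits correction because the correction is cheap and completes the safety record that the protocol itself asks for.

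**What to change.** Reconcile Sections 4.7, 5.1, 5.4, 5.2.5 and 7.6.1 to one window by setting the existing final safety contact at POD 37 or later for all patients.
- In Section 4.7, carry adverse-event follow-up to that contact.
- In Section 5.1, move the last column and footnote 1 from POD 30 to POD 37 or later, and state that SAEs and concomitant medications are asked about at that contact.
- In Section 5.4, change the minimum to match.
- In Sections 5.2.5 and 7.6.1, keep the 30-day windows and refer to this contact as the point at which they are checked.

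A fixed day is better than 30 days after each patient's own last dose. Both close the gap, but the second makes minimum follow-up depend on dosing duration (POD 35 for a last dose on POD 5, POD 37 for one on POD 7). A common POD 37 covers 30 days after the latest possible dose and keeps minimum follow-up equal across patients and arms. It also leaves 60 − 37 = 23 days for contact attempts before the limit in Section 5.5.8.

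The cost is a close-out up to a week later per patient, and one added phone call for patients whose routine clinic visit falls on POD 30–36 and would no longer serve as the final contact. Sample size and the efficacy analysis do not change.

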### **7.6.2 Routine Reporting Requirements**

- The UCSD HRPP will be notified of any adverse events that are not unanticipated problems involving risk to subjects or others (non-UPRs) at the time of the annual Continuing Review.

## **8.0 AGENT INFORMATION**

---

### **8.1 Agent Alvimopan**

Please refer to Prescribing Information for more comprehensive information.

**Other names for the drug:** Entereg®

**Mechanism of action (or Product description):**

Alvimopan is a peripherally acting mu-opioid receptor antagonist, blocking the peripheral effects of opioids on gastrointestinal motility and secretion but not the central analgesic effects of mu-opioid agonists.

**Availability:**

Alvimopan (and placebo) will be provided by the sponsor free of charge.

**How supplied:**

Alvimopan will be supplied as 12 mg oral capsules by the sponsor. Unmatched placebo capsules will also be supplied, and alvimopan and placebo will be over-encapsulated by UCSD pharmacy to maintain double-blinding.

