#### **4.5 Toxicities and Dosing Delays/Dose Modifications**

Any patient who receives treatment on this protocol will be evaluable for toxicity. Each patient will be assessed for the development of toxicity according to the NCI Common Toxicity Criteria for Adverse Events (CTCAE), version 4.03. Dose adjustments are not applicable in this study and will not be made. Participants who have emesis within one hour after taking the study medication or have visible study medication within the gastric tube effluent or who otherwise miss a dose for any other reason, will not be re-dosed, and they will resume standard dosing at the next scheduled dose. Participants or providers may decide to cease the study medication before all doses have been administered per the criteria listed in Section 4.6.

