**Route of administration for this study:**

Study drug (alvimopan or placebo) will be administered orally. If a gastric or nasogastric tube is present, it will be clamped for one hour after oral administration of the study drug.

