**9.1 Study Design/Study Endpoints**

The proposed study is a double blind prospective, randomized controlled phase 2 trial.

Subjects will be assigned 1:1 to either placebo or alvimopan groups using a permuted block randomization of block size 4. The block and package in the R statistics software will be used to generate group assignments. The randomization file will be given to the investigational Pharmacy which will carry out the randomization. Patients who do not undergo CRS/HIPEC during surgery are considered screen failures after randomization. Their randomization IDs will not be discarded and will be passed to the next available subjects to keep the 1:1 ratio.

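### A fixed block of 4 printed in the protocol, and re-used randomization IDs, make allocation more predictable than it need be if a capsule is ever seen

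*Combined protocol and SAP*

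**What the plan says.** **Capsules.** Section 8.1 (How supplied) says: "Unmatched placebo capsules will also be supplied, and alvimopan and placebo will be over-encapsulated by UCSD pharmacy to maintain double-blinding". The documents do not describe the shell or the fill, and they do not say what to do if an inner capsule becomes visible.

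**Possible exposure.** Section 4.5 covers patients who vomit within an hour of a dose or who "have visible study medication within the gastric tube effluent". Its only instruction is that they "will not be re-dosed, and they will resume standard dosing at the next scheduled dose". Section 8.1 (Route of administration) adds: "If a gastric or nasogastric tube is present, it will be clamped for one hour after oral administration of the study drug".

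**Allocation.** Section 9.1 says: "Subjects will be assigned 1:1 to either placebo or alvimopan groups using a permuted block randomization of block size 4". It also says: "The randomization file will be given to the investigational Pharmacy which will carry out the randomization". The Study Summary names one center, and no stratification factor is stated. IDs of randomized patients who do not undergo CRS/HIPEC are kept and "will be passed to the next available subjects to keep the 1:1 ratio".

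**Endpoints.** Under section 6.1, GI-2 needs both a first bowel movement and solid food tolerated over a 4-hour window. Under section 6.1.2, time to discharge ends when the order is signed.

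**The concern.** The blind holds while the outer shell hides the inner capsule. If the shell opens and the inner capsule can be recognized, ward staff may learn one patient's arm. Two rules in section 9.1 can then pass that knowledge on to patients whose capsules nobody saw. With a known block of 4, one arm is informative about the next. With a passed-on ID, the next holder receives the same arm.

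This matters because staff influence part of what is measured. Solid food has to be offered before it can be tolerated, and a clinician signs the discharge order. A belief about the arm could shift either time. The re-use rule also has a side effect. Section 9.4 keeps dosed screen failures in the Safety population, so two dosed people in that population can share one randomization ID.

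**Working it through.** **Inputs.** Block size 4, ratio 1:1, list held by pharmacy (section 9.1); one center (Study Summary); 128 participants (section 9.2). The proportion *q* of allocations that become exposed is not in the documents. I assume 10% and 30%, with 5% and 50% as outer values. The plan gives no figure for predictability or for the quality of the blind, so there is none to reproduce. The sample size does not depend on this point.

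**1. One exposed allocation.** A balanced block of 4 has six equally likely orders: AAPP, APAP, APPA, PAAP, PAPA, PPAA. Of the three that start with A, two have P second. So P(next is opposite, given one known arm in the same block) = 2/3, or odds of 2:1 instead of 1:1. If the position in the block is unknown, the next patient may start a new block: 3/4 × 2/3 + 1/4 × 1/2 = 0.625.

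**2. Worst case, every earlier arm in the block known.**
- Best-guess accuracy by position is 1/2, 2/3, 2/3 and 1. The mean is (1/2 + 2/3 + 2/3 + 1)/4 = 17/24 = 70.8%.
- Certain calls by position are 0, 0, 1/3 and 1. The mean is (4/3)/4 = 33%, or 128/3 ≈ 43 patients.

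**3. Partial exposure, block positions known.** Accuracy by position:
- position 1: 1/2
- position 2: 1/2 + q/6
- position 3: 1/2 + [1 − (1 − q)²]/6
- position 4: (1/2)(1 − q)³ + (2/3)[3q(1 − q)² + 3q²(1 − q)] + q³

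The proportion of certain calls is (q²/3 + q²)/4 = q²/3. For q = 0.10, accuracy is (0.5000 + 0.5167 + 0.5317 + 0.5455)/4 = 0.523. For q = 0.30, it is (0.5000 + 0.5500 + 0.5850 + 0.6185)/4 = 0.563.

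| Assumed q | Correct guesses | Certain calls |
|---|---|---|
| 5% | 51.2% | 0.1% |
| 10% | 52.3% | 0.3% |
| 30% | 56.3% | 3.0% |
| 50% | 59.9% | 8.3% |
| 100% | 70.8% | 33.3% |

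**4. Re-used ID.** The next holder has the same arm with probability 1. For an observer to use this, the first holder's arm must be known and the ID must be linked to its new holder. Footnote 5 of the Schedule of Events has CRS/HIPEC confirmed on POD 1 before any postoperative dose. A patient whose ID is passed on has therefore had at most the single preoperative dose. The documents give no probability for either condition.

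**5. What varying blocks would gain.** Simulation (5,000 runs of 128 patients), always guessing the arm that is behind, with all earlier arms known:

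| Block sizes | Correct guesses | Next patient opposite, position unknown |
|---|---|---|
| Fixed 4 | 70.8% | 62.5% |
| Random 2/4/6 | 70.2% | 62.6% |
| Random 4/6/8 | 67.9% | 58.3% |

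Average guessing improves little, and not noticeably if blocks of 2 are in the mix. The main gain is that an observer no longer knows where a block ends, so certain calls largely go. I have not quantified that part.

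**The case against.** Over-encapsulation by pharmacy is a recognized method and is the plan's own answer to unmatched capsules. For exposure to matter, an inner capsule must stay recognizable after an hour with the tube clamped. The observer must also know which appearance belongs to which arm, and must know the order of randomization. Pharmacy holds the list, and nothing says that ward staff see inner capsules, sequence or IDs. The bowel movement component of GI-2 is harder for staff to influence. Event times come from a patient diary (Appendix B) that is audited against the chart in at least 10% of participants, and section 4.4 describes a standardized care pathway. All of this stands, and it keeps the point small.

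A reader might infer three stronger things, and the documents support none of them:
- *Staff are told to look for study drug.* Section 4.5 orders no search; it says only what happens to dosing if drug is seen.
- *One exposed allocation reveals the next.* For the block it gives 2:1 odds. Only a re-used ID carries certainty, and only under the two conditions in step 4. Knowing whose CRS/HIPEC was not done does not show who inherits the ID.
- *A third of allocations are predictable.* The 33% and 71% need every earlier arm in the block to be known.

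The objection does not supply a reason for the two rules in section 9.1 beyond keeping the arms equal, and exact equality is worth very little here.

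**Conclusion.** This is a minor but valid design point. A fixed, printed block of 4 and re-used IDs add avoidable predictability to a blind that depends on an outer shell. On assumed exposure of 10 to 30%, correct guesses rise from 50% to about 52 to 56%, with 0.3 to 3.0% of allocations certain; 71% is the ceiling. These figures assume an observer who knows the block size and positions and guesses optimally, so they lean high for real ward staff. The exposure rate itself is my assumption.

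The documents do not show that the blind fails, or that the primary result would be biased. Whether an inner capsule could be recognized in effluent cannot be settled from them.

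**What to change.** Change section 9.1 in two places:
1. Use randomly varying block sizes, held only in the pharmacy randomization file, and remove the block size from the protocol. Deleting the figure alone is not enough, since staff may already have read it. On the figures above, 4/6/8 does better than a mix that includes 2.
2. Give each replacement the next unused ID and retire the ID of the patient who did not undergo CRS/HIPEC. The list then needs spare entries beyond 128.

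**Cost.** A new list for the patients still to be randomized, and an amendment to one paragraph. Appendix C gives an activation date of 02/28/2018, so this may be a mid-trial change that applies to the remaining list only. Final arm sizes may differ by a few patients. As an illustration, a 61:67 split keeps 4 × 61 × 67/128² = 16,348/16,384 = 99.8% of the information of an equal split, so the power loss is negligible.

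**What not to rely on.** A yes/no log of capsule sightings would be useful as description only. An analysis that drops those patients selects on a post-randomization event and should not be used to support the primary result. Matching the inner capsules would help, but depends on supply.
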